8.4. Other Secondary Endpoints

Other secondary endpoints are PFS according to RECIST v1.1 guidelines, as assessed by the local Investigator's review, and ORR (confirmed CR + confirmed PR) according to RECIST v1.1 guidelines, as assessed by the local Investigator's review. Additionally CBR, DCR, time to response and duration of response will be analyzed. These analyses will be supportive in nature and, hence, will not be subject to Type I error control. Statistical tests will be 2-sided with a nominal Type I error rate of 0.05.

PFS and ORR as assessed by investigator, will be analyzed as described in Section 8.1.3 for the ITT (3rd line+) set. Date of Progression will be the date assessed by the investigator.

CBR and DCR will be analyzed in ITT (3rd line+) set and RE (3rd line+) set. Time to response and duration of response will be analyzed only in RE (3rd line+) set. These analyses will be performed for parameters defined from the best responses as assessed by (i) the IRC and (ii) the local Investigator's review.

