5. STUDY POPULATION

5.1 Patient Inclusion Criteria

Patients with measurable and non-measurable disease will be eligible for inclusion in this study only if all the following criteria are met:

- 1. Patients at least 18 years of age (or according to local regulation).
- 2. Documented histologically confirmed BC.
- 3. Metastatic BC currently of stage IV disease by American Joint Committee on Cancer criteria or unresectable locoregionally recurrent BC.
- 4. Molecular status and prior therapies:
 - a) Molecular Status
 - Eligible patients are, by their patient records and prior therapy, HER2 negative with any ER or PgR status. If a previous record of the HR status is not available, the HR status should be tested locally.
 - HER2 negative (IHC 0,1 or fluorescence in situ hybridization [FISH] or chromogenic in situ hybridization [CISH] HER2:CEP17 ratio < 2.0); HER2 2+ patients should be FISH/CISH negative.
 - b) Prior Therapies
 - Patients with locally recurrent or metastatic BC who have previously received 1–4 chemotherapeutic regimens for the treatment of locally recurrent or metastatic BC. Unless contra-indicated for safety reasons, prior therapy will have included an anthracycline and a taxane in either the adjuvant or metastatic setting.
 - Patients with HR positive status (ER+ and/or PgR+) must have been treated with at least one line of endocrine therapy and considered by the treating physician not to be a candidate for further endocrine therapy.
- 5. At least 14 days from the completion of any previous cytotoxic chemotherapy, biological therapy, or any other investigational agent at time of initiation of study medication. Resolution of chemotherapy and radiation therapy related toxicities to Grade 1 or lower severity, except for stable sensory neuropathy Grade 2 or lower and alopecia.
- 6. Patients must have proved refractory to the most recent chemotherapy, documented by progression on or within six (6) months of therapy.

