8.2.2 Post-baseline Tumor Assessments

Tumor assessments are to be scheduled using the randomization date as the reference date for all timepoints; tumor assessments are NOT to be scheduled according to the timepoint of the previous tumor assessment.

Protocol No.: POL6326-009

Version 3.0

From the date of randomization, patients will be evaluated according to RECIST v1.1 for CR, PR, SD, or PD based on CT/MRI scans performed every 6 weeks (±7 days) during the first year, and then every 12 weeks (±7 days), thereafter, until PD is documented by RECIST v1.1. The RECIST v1.1 definitions of the criteria used to determine tumor response for target lesions are provided in Table 5 and for non-target lesions in Table 6. Table 7 provides a summary of the overall response calculation that is to be used at each response assessment timepoint specified in the Study Schedule for patients who have measurable disease at baseline. When patients have non-measurable disease only, Table 8 is to be used. Further information is summarized in Appendix 3 Summary of RECIST v1.1 Guidelines.

Table 5 Determination of Objective Tumor Response for Target Lesions

Tumor Response	Evaluation of Target Lesions
Complete Response (CR)	Disappearance of all target lesions. Any pathological lymph nodes (whether target or non-target) must have reduction in short axis to <10 mm.
Partial Response (PR)	At least a 30% decrease in the sum of diameters of target lesions, taking as reference the baseline sum diameters.
Progressive Disease (PD)	At least a 20% increase in the sum of diameters of target lesions, taking as reference the smallest sum of diameters of target lesions recorded on study (this includes the baseline sum if that is the smallest on study). In addition to the relative increase of 20%, the sum must also demonstrate an absolute increase of at least 5 mm. (Note: the appearance of one or more new lesions is also considered progression).
Stable Disease (SD)	Neither sufficient shrinkage to qualify for PR nor sufficient increase to qualify for PD, taking as reference the smallest sum diameters while on study.

Source: (55)

Further details can be found in Appendix 3 Summary of RECIST v1.1 Guidelines.

Protocol No.: POL6326-009

Version 3.0

Table 6 Determination of Tumor Response for Non-target Lesions

Tumor Response	Evaluation of Non-target Lesions

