The local Investigator will assess the presence of disease following CT/MRI scan performed at Screening, and those performed subsequently, and record the details in the patient's source data and eCRF relative to the previous assessment of disease status/metastatic burden.

Following initial documentation of an objective response, a confirmatory CT/MRI scan will be performed at least 4 weeks later.

Patients will continue treatment as assigned at randomization until objective PD (according to RECIST v1.1) is documented, there is unacceptable toxicity, death occurs, the patient withdraws consent, or the patient is lost to follow-up (whichever occurs first).

CT/MRI will be performed at the EoT visit in patients who are discontinued from study medication in the absence of PD; however, patients who have already demonstrated objective PD according to RECIST v 1.1 do not need to have scans repeated at the EoT visit.

Regardless of regimen, patients who are discontinued from study medication for any reason in the absence of PD, will also undergo repeat imaging and tumor response assessments (including CT/MRI scans) every 8 weeks ±7 days (every 12 weeks [±7 days] if the patient has been on the study for ≥1 year), until PD is documented as per RECIST v1.1, or death occurs, or patient is lost to follow-up, or the patient withdraws consent (whichever occurs first). If a patient stops study medication and begins another anti-cancer therapy before PD is documented, every effort should be made to perform tumor evaluation in these patients until disease progression. Every effort should be made to collect and record all anti-cancer medicines that the patient receives during Long-term Follow-up in the patient's source data and eCRF until the end of the study.

a. `Non-CR/Non-PD' is preferred over `stable disease' for non-target disease because SD is used as an endpoint for assessment of efficacy so to assign this category when no lesions can be measured is not advised.

Protocol No.: POL6326-009

Version 3.0

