12.2.7.4 Other Secondary Endpoints

Analysis of the other secondary endpoints in the overall, 2nd line + population, i.e. ORR, CBR, DCR, time to response, and duration of response will not be subject to Type I error control. Statistical tests will be 2-sided with a nominal Type I error rate of 0.05.

ORR will be analyzed by exact logistic regression and be stratified for randomization stratification factors. The odds ratio will be estimated from the model along with the associated 95% CI and 2-sided p-value. Exact Clopper-Pearson 2-sided 95% CI limits will be calculated for the proportion of patients with ORR in each arm.

ORR analyses will be performed for the Response Evaluable Population. Patients who do not have measurable disease at baseline will be excluded from the population. In addition to presenting ORR, the best response using response categories CR, PR, SD, PD, and not evaluable (NE) will be tabulated. The proportion of the response in each response category will be calculated. Patients who do not have any post-baseline tumor assessment will be counted under the category NE. SD requires at least one post-baseline scan performed at 6 weeks (42 days) or later. Patients who did not have any post baseline scans for the 6 week assessment or later, and who also do not have a documented PD will be counted as NE.

Duration of response will be analyzed in the Response Evaluable Population, and CBR will be analyzed in both the Response Evaluable Population and ITT population.

CBR will be compared between the treatment arms using exact logistic regression as described for ORR. Exact Clopper Pearson 2-sided 95% confidence limits will be calculated for the CBR of each treatment arm.

Duration of response will be analyzed via Cox regression modelling with a fixed effect term for randomized treatment. The hazard ratio will be estimated from the model along with the associated 95% CI and 2-sided p-value. The data will also be displayed using Kaplan-Meier curves; median duration of response and the 95% CIs will be estimated from the Kaplan-Meier

Protocol No.: POL6326-009

Version 3.0

by treatment arm. A supportive analysis will be performed based on the expected duration of response as per Ellis et al (2008) (59).

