4.3.6. Response Evaluable Set (3rd Line+)

The Response Evaluable (RE) set (3rd line+) will be used to evaluate disease response. The RE set (3rd line+) includes all randomized patients in the 3rd line+ population with measurable disease by RECIST v1.1 as determined by the Investigator at screening during the evaluation of breast cancer history. The co-primary endpoint analysis of ORR and other secondary endpoint analyses of CBR, duration of response, DCR and time of response will be conducted using the RE (3rd line+) set. Patients will be analyzed by the treatment arm to which they are randomized.

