The number of patients experiencing events and the number of censored patients will be summarized by randomized treatment arm with reasons for an event/censoring. The median survival times will be estimated by the Kaplan-Meier method and presented along with their corresponding 95% CI. The 25th percentile and 75th percentile for the survival times along with the corresponding 95% CI for the percentiles will also be displayed, CI will be calculated using method of Brookmeyer and Crowley (1982). Additionally, PFS probabilities at fixed time points i.e. 3, 6, 9, 12, 15 months will be derived from the Kaplan-Meier estimates with 95% confidence intervals, CI will be calculated using the Greenwood formula. The time points will be displayed based on the data availability.

Corresponding plots of Kaplan-Meier curves by treatment arm will also be presented. The plots will display the number of patients at risk every 3 months. Alongside this the PFS data will be presented in a listing by treatment arm.

Objective Response Rate

The ORR, defined from the best response as assessed by the IRC, will be analyzed by an exact logistic regression, stratified for randomization stratification factors excluding line of therapy (see Section 4.2 for further details). The odds ratio will be estimated from the model along with the associated 99.9% CI (0.001 alpha) and 2-sided p-value. Exact Clopper-Pearson 2-sided 95% confidence limits will be calculated for the proportion of patients with objective response in each arm.

ORR analyses will be performed for the RE (3rd line+) set and RE (3rd line+ Confirmed) set. Analysis of the RE (3rd line+ Confirmed) set is added as sensitivity and is not part of the alphacontrol for this study. In addition to presenting ORR, the best response as assessed by the IRC using response categories CR, PR, SD, PD and NE will be summarized. The number and percentage of patients in each response category will be presented by treatment arm. Patients who do not have any post-baseline tumor assessment will be counted under the category NE. SD requires at least one post-baseline scan performed at minimum of six (6) weeks (42 days) +/- seven (7) days, for a minimum time on-study of thirty-five (35) days or later. Patients who did not have any post baseline scans for the 6-week assessment or later and also do not have a documented PD will be counted as NE.

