8.4.3. Clinical Benefit Rate

Clinical benefit rate (CBR) is defined as the proportion of patients with a confirmed CR, confirmed PR, or SD for at least 6 months (\geq 182 days).

The CBR, as assessed according to RECIST v1.1 guidelines by the IRC, will be analyzed for RE $(3^{rd} line+)$ and ITT $(3^{rd} line+)$ analysis sets using an exact logistic regression as described for ORR in Section 8.1.3.

The CBR, as assessed by local investigator's review, will also be analyzed will be analyzed for RE (3rd line+) and ITT (3rd line+) analysis sets using an exact logistic regression as described for ORR in Section 8.1.3.

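### In the ITT set, CBR and DCR have no rule for Non-CR/Non-PD, so a stable patient with only non-measurable disease counts as a failure if the definitions are followed literally

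*SAP*

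**What the plan says.** - **Eligibility.** Protocol 5.1: "Patients with measurable and non-measurable disease will be eligible for inclusion in this study only if all the following criteria are met".
- **Scoring.** Protocol 8.2.2: "When patients have non-measurable disease only, Table 8 is to be used". Table 8 has four outcomes: CR, Non-CR/Non-PD, not evaluable and PD. It has neither PR nor SD. Its footnote explains the absence of SD: "SD is used as an endpoint for assessment of efficacy so to assign this category when no lesions can be measured is not advised".
- **Definitions.** CBR (SAP 8.4.3) counts confirmed CR, "confirmed PR, or SD for at least 6 months", with six months set at 182 days. DCR (SAP 8.4.4) counts confirmed CR, confirmed PR or SD of whatever length. Protocol 8.3.6 and 8.3.7 use the same components.
- **Analysis sets.** SAP 8.4: "CBR and DCR will be analyzed in ITT (3rd line+) set and RE (3rd line+) set", each by IRC and by investigator. Protocol 12.2.7.4 agrees for CBR: "CBR will be analyzed in both the Response Evaluable Population and ITT population". SAP 4.3.6, however, assigns both endpoints to the response evaluable (RE) set alone, that is, to patients "with measurable disease by RECIST v1.1 as determined by the Investigator at screening".
- **Best response.** Under SAP 8.1.3 the IRC best response "using response categories CR, PR, SD, PD and NE will be summarized". The investigator algorithm in SAP Appendix 14.5 ranks CR, PR, SD, PD and lists 17 cases. None of them covers Non-CR/Non-PD.

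**The concern.** The definitions of CBR and DCR suit patients whose lesions can be measured, because SD is available to them. The ITT set adds patients for whom the protocol's own table does not offer SD, and the definitions were not adapted. A patient with, say, only ascites or lymphangitic disease who remains Non-CR/Non-PD for a year has had what both endpoints are meant to capture, yet fits none of the success categories.

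NE does not fit either: SAP 8.1.3 reserves it for patients with no post-baseline assessment, or with no scan at six weeks or later and no documented PD.

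At stake is whether the ITT rates mean what their names say, and whether two programmers working from the same SAP would produce the same table.

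**Working it through.** **Plan's own figure.** Neither document gives a planned rate or power for CBR or DCR. The SAP's 286 PFS events reproduce with the Schoenfeld formula (hazard ratio 0.674, 1-sided 2.0%, 90% power), but that figure does not bear on this point.

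**Inputs.** For illustration, CBR is 17% on eribulin alone (literature figure in Protocol 2.2) and 44% on the combination (Phase 1 Overall Efficacy Population, Protocol 2.5.1). The share *m* of ITT patients with only non-measurable disease is not in the documents; 10–30% is assumed.

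**Formula.** Let *p* be the rate in measurable patients, and *q* the proportion of non-measurable patients who would meet the endpoint through Non-CR/Non-PD. For simplicity, suppose none of the latter reaches CR.

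- Rate with Non-CR/Non-PD credited: (1 − m)p + mq
- Rate as defined, read literally: (1 − m)p
- Shortfall in an arm: mq
- Change in the treatment difference: −(m_T q_T − m_C q_C), where T is the combination and C is eribulin alone

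**Case 1: same true rates in both kinds of patient (q = p), same share in both arms.**

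| m | Eribulin | Combination | Difference (points) | Odds ratio |
|---|---|---|---|---|
| Non-CR/Non-PD credited | 17.0% | 44.0% | 27.0 | 3.84 |
| 10% | 15.3% | 39.6% | 24.3 | 3.63 |
| 20% | 13.6% | 35.2% | 21.6 | 3.45 |
| 30% | 11.9% | 30.8% | 18.9 | 3.30 |

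At 20%, for example, 0.8 × 17 = 13.6 and 0.8 × 44 = 35.2. With the Phase 1 Expanded Cohort's 63% instead of 44%, the difference goes from 46.0 to 36.8 points at 20%. The documents give no DCR; with an assumed 55% versus 70%, the rates become 44.0% and 56.0% at 20%, and the difference goes from 15.0 to 12.0 points.

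**Case 2: no treatment effect in non-measurable patients (q = 17% in both arms, m = 20%).** Credited: 0.8 × 44 + 0.2 × 17 = 38.6 and 0.8 × 17 + 0.2 × 17 = 17.0, a difference of 21.6. As defined: 35.2 − 13.6 = 21.6. The rates fall, but the difference does not change.

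**Case 3: reverse effect in non-measurable patients (q = 10% on the combination, 17% on eribulin, m = 20%).** Credited difference: 21.6 − 0.2 × 7 = 20.2. As defined: 21.6, which is too large.

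**Case 4: unequal shares (m = 15% on the combination, 25% on eribulin; q = p).**

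- Both true CBRs 17%: 0.85 × 17 − 0.75 × 17 = 1.7 points where there is no difference.
- CBR 17% versus 25%: 0.85 × 25 − 0.75 × 17 = 8.5 points against a true 8.0.
- DCR 55% versus 70% (assumed): 0.85 × 70 − 0.75 × 55 = 18.25 points against a true 15.0.

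Measurability is not among the stratification factors in SAP 4.2, so randomization does not specifically guard against such an imbalance.

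**The case against.** **SD is not forbidden.** The Table 8 footnote gives advice, not a prohibition. SAP section 8 expects the IRC to return CR, PR, SD, PD or NE, so Non-CR/Non-PD might in practice be recorded as SD. The imaging plan and the eCRF page, which might settle this, are not among the documents. A reader might infer that these patients can never be SD and are certain to be counted as failures; the text does not go that far, and they can also succeed through confirmed CR. What stands is that the written rules, followed as they are, give Non-CR/Non-PD no credit, and that nothing written maps it to SD.

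**The direction for the treatment comparison is not fixed.** A reader might infer that the difference between arms is understated. That needs a favourable effect in non-measurable patients and similar shares by arm; Cases 2 to 4 show no change or inflation when either condition fails. This part of the objection stands in full.

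**Size.** One could instead use the planned exponential PFS curve, under which 34.6% of eribulin patients are progression-free at 182 days; a 20% share would then cost 6.9 points. That puts PFS in place of CBR. With the protocol's cited CBR of 17%, the loss is 3.4 points.

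**The RE analysis already exists.** It excludes patients whom the investigator judges non-measurable, so it is largely unaffected. It is not fully protected, because a patient measurable to the investigator but not to the IRC could still be Non-CR/Non-PD in the IRC analysis. Nor does it repair the ITT result, which SAP 8.4 calls for alongside it.

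**Conclusion.** The point holds as a mismatch between the stated definitions and the stated analysis set. Read literally, the ITT CBR and DCR are understated in each arm by the share of patients with only non-measurable disease who would meet the endpoint through Non-CR/Non-PD. With equal true rates and a 20% share, the CBR shortfall is 3.4 points from 17% and 8.8 points from 44%; over a 10–30% share it is 1.7 to 5.1 and 4.4 to 13.2 points. These sizes rest on the assumed share and on CBR figures from outside this trial.

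No direction can be stated for the treatment difference. It shrinks in proportion to the non-measurable share only if that share is balanced and the effect is the same in these patients.

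The consequence is limited. Both endpoints are supportive and outside Type I error control. ORR in the RE set, PFS, OS and the alpha scheme are not touched.

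**What to change.** Before the analysis:

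1. In SAP 8.4.3 and 8.4.4, for the ITT analyses by IRC and by investigator, count Non-CR/Non-PD lasting at least 182 days as clinical benefit, and Non-CR/Non-PD that meets the 35-day minimum used for SD as disease control. Align Protocol 8.3.6 and 8.3.7.
2. Add Non-CR/Non-PD to the derivation in Appendix 14.5 and to a best-response table for the ITT set.
3. Report the share of patients with only non-measurable disease by arm.
4. Reconcile SAP 4.3.6 (RE only) with SAP 8.4 (ITT and RE).

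Leave the RE population and its definitions as they are.

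The cost is SAP wording, matching wording in two protocol definitions, a derivation change and one more table. No further patients or assessments are needed, provided that the Table 8 outcome is recorded by the IRC and in the eCRF; the documents do not show this, so it should be checked first.

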8.4.1. PFS Assessed by Local Investigator's Review

PFS, as assessed by local Investigator's review, will be analyzed as described in section 8.1.3. The date of assessment used will be the date recorded in the eCRF page "Overall Response according to RECIST v1.1 assessment".

8.4.2.ORR Assessed by Local Investigator's Review

ORR, as assessed by local investigator's review, will be analyzed as described in section 8.1.3. It will be defined as the proportion of patients with a confirmed CR or a confirmed PR according to RECIST v1.1 based upon the best response assessed, as assess by local investigator's review. The confirmed responses (best responses) are not entered in the eCRF, the algorithm for the best response determination according to RECIST v1.1 guidelines, as assessed by the local Investigator's review, can be found in Appendix 14.5.

The Date of First Response is defined as the time point response (TPR) date when the criteria for CR or PR were first met, whichever status is recorded first, for subjects whose confirmed response (Best Response) is either a CR or a PR. The Date of First Response may or may not be the same as the Date of Best Response.

8.4.3. Clinical Benefit Rate

Clinical benefit rate (CBR) is defined as the proportion of patients with a confirmed CR, confirmed PR, or SD for at least 6 months (\geq 182 days).

The CBR, as assessed according to RECIST v1.1 guidelines by the IRC, will be analyzed for RE $(3^{rd} line+)$ and ITT $(3^{rd} line+)$ analysis sets using an exact logistic regression as described for ORR in Section 8.1.3.

The CBR, as assessed by local investigator's review, will also be analyzed will be analyzed for RE (3rd line+) and ITT (3rd line+) analysis sets using an exact logistic regression as described for ORR in Section 8.1.3.

8.4.4. Disease Control Rate

Disease control rate (DCR) is defined as the proportion of patients with a confirmed CR, confirmed PR, or SD of any duration. Patients with SD of any duration as the best response will be considered for this analysis and not only patients with SD of confirmed best response.

The DCR, as assessed by IRC, will be analyzed for RE (3rd line+) and ITT (3rd line+) analysis sets using an exact logistic regression as described for ORR in Section 8.1.3

The DCR, as assessed by local investigator's review, will also be analyzed will be analyzed for RE (3rd line+) and ITT (3rd line+) analysis sets using an exact logistic regression as described for ORR in Section 8.1.3.

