12	SD	PD	SD or PD
			SD, if SD assessment >=6 weeks (+/-7 days), i.e. 35 days after date of randomization,
			otherwise PD
13	SD	NE	SD or NE
			SD, if SD assessment >=6 weeks (+/-7 days), i.e. 35 days after date of randomization,
			otherwise NE
14	CR, PR, SD	-	SD or NE
			SD, if assessment >=6 weeks (+/-7 days), i.e. 35 days after date of randomization and does not qualify for CR or PR,
			otherwise NE.
15	PD	No further	PD. Ignore all assessments after initial overall response of PD.

	Overall response entered in eCRF by investigator		
Case	First Time Point Response (TPR)**	Subsequent Time Point Response (TPR)	Confirmed Response (Best Response)*
16	NE	NE	NE Where all assessments are Not evaluable
17	NE	-	NE

* A Best Response of SD can only be made after the subject is on-study for a minimum of six (6) weeks (42 days) +/- seven (7) days, for a minimum time on-study of thirty-five (35) days. If the subject is on-study less than six (6) weeks (42 days) +/- seven (7) days or thirty-five (35) days, any tumor assessment indicating Stable Disease before this time period will have a Best Response of NE unless PD is identified.

** For this study, up to three (3) intervening NEs will be allowed between CRs or PRs but only one (1) intervening SD is allowed between PRs. Subsequent documentation of CR may provide confirmation of a previously identified CR for subjects where the intervening integrated responses, up to three (3), were NE. Subsequent documentation of PR may provide confirmation of a previously identified PR for subjects where the intervening integrated responses, up to three (3), were NE. If the post-NE TPR confirms the CR (or PR) then the Confirmed Response will be CR (or PR). For example, CR NE CR = confirmed CR, CR NE NE CR = confirmed CR, or CR NE NE NE CR = confirmed CR ; PR NE PR = confirmed PR, PR NE NE PR = confirmed PR, or PR NE NE NE PR = confirmed PR ; CR SD CR \neq confirmed CR ; PR SD PR = confirmed PR. Note: in the following scenario, PR SD NE PR, the second PR is not a confirmed PR.

(1) TPR is SD if the increase from the first to the second assessment does not qualify for PD.

The confirmed response (best response) is defined when all Overall response assessments have been reviewed.

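### SAP 8.4.4 lets stable disease of any duration count as disease control, although the SAP's own best-response rules do not accept SD before day 35

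*SAP*

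**What the plan says.** **DCR.** SAP 8.4.4 opens: "Disease control rate (DCR) is defined as the proportion of patients with a confirmed CR, confirmed PR, or SD of any duration". A second sentence widens this: "SD of any duration as the best response will be considered for this analysis and not only patients with SD of confirmed best response". DCR is analysed in the ITT (3rd line+) and Response Evaluable (3rd line+) sets, once by independent review and once by the investigator. SAP 8.4 says these response parameters are taken from the best responses.

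**Best response, independent review.** In SAP 8.1.3, "SD requires at least one post-baseline scan performed at minimum of six (6) weeks (42 days) +/- seven (7) days". The same sentence then gives the resulting floor: "for a minimum time on-study of thirty-five (35) days or later". Patients with no post-baseline "scans for the 6-week assessment or later and also do not have a documented PD will be counted as NE".

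**Best response, investigator.** In Appendix 14.5, case 12 (SD followed by PD) gives "SD, if SD assessment >=6 weeks (+/-7 days), i.e. 35 days after date of randomization", and PD otherwise. Cases 13 and 14 use the same threshold with NE as the alternative. The footnote adds that "any tumor assessment indicating Stable Disease before this time period will have a Best Response of NE unless PD is identified".

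**Protocol.** Section 8.3.7 defines DCR under RECIST v1.1 as confirmed CR, confirmed PR or SD, and does not say that SD may be of any duration. Table 17 in Appendix 3 makes SD conditional on a minimum duration. Section 12.2.7.4 asks for a scan at day 42 or later, and 12.3.7.4 carries the same methods to the third-line-plus population. On imaging, section 8.2.2 states: "CT/MRI will be performed at the EoT visit in patients who are discontinued from study medication in the absence of PD".

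**The concern.** The same SAP gives one patient two SD statuses: not SD in the best-response table, but SD for DCR. The DCR numerator then need not equal CR + PR + SD in the best-response table built from the same scans.

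The patients added are those with very short observed stability, and such scans arise by design. Anyone stopping treatment without PD is scanned at the end-of-treatment (EoT) visit, within 7 days of stopping (protocol 7.6). Unscheduled scans are allowed on clinical suspicion of progression. After an early stop, follow-up imaging is every 8 weeks (protocol 7.8.1), and scans after new anti-cancer therapy are excluded from response derivation (SAP 8.1.2). An early SD scan can therefore be the only usable one.

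At stake is whether a reported DCR means control of disease to at least the first scheduled assessment, or merely one early scan without progression. If the two arms differ in how many such patients they have, the DCR comparison shifts for a reason unrelated to disease control.

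**Working it through.** **1. The threshold.** 42 days − 7 days = 35 days. This reproduces the SAP's figure.

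**2. The rules applied to example scan sequences.** Take a patient who stops treatment on day 15. The EoT scan falls by day 15 + 7 = day 22. If 8 weeks are counted from that scan, the next is at about day 22 + 56 = day 78. Counting from randomization gives another date, but still after day 35. All scans are taken as before any new therapy. Best response follows Appendix 14.5.

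| Scans | Best response (case) | DCR from best response | DCR as 8.4.4 reads |
|---|---|---|---|
| SD day 22 only | NE (14) | no | yes |
| SD day 22, NE day 78 | NE (13) | no | yes |
| SD day 22, PD day 78 | PD (12) | no | yes |
| SD day 34 only | NE (14) | no | yes |
| SD day 35 only | SD (14) | yes | yes |
| SD day 22, SD day 78 | SD (11) | yes | yes |
| PR day 22 only | NE (14) | no | no |

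The first four rows diverge. Divergence needs an SD scan before day 35 and no further SD scan at day 35 or later before new therapy. The sixth row shows that an early EoT scan alone is not enough.

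The last row is an anomaly. Read literally, a single day-22 scan showing PR is neither a confirmed PR nor SD and fails DCR, while an unchanged scan on the same day passes.

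**3. Which review gives which result.** SAP 8.1.3 states the NE outcome for independent review when there is no scan from day 35 and no PD (rows 1 and 4). The PD outcome in row 3 is spelled out only in Appendix 14.5, the investigator algorithm.

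**4. Size per patient.** The plan has 320 third-line-plus patients randomized 1:1, so an even split gives 320 / 2 = 160 per arm. One patient moves an arm's DCR by 100 / 160 = 0.625, about 0.63 points. The Response Evaluable set is limited to measurable disease, so its denominator can only be the same or smaller and the step the same or larger.

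**5. Illustrative range.** The documents give no count of such patients. Assuming 1 to 8 in an arm:

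- that arm's DCR rises by 1 × 0.625 = 0.6 to 8 × 0.625 = 5.0 points;
- 8 versus 2 shifts the difference by (8 − 2) × 0.625 = 3.75 points;
- 8 versus 8 shifts it by 0.

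For scale, with an assumed DCR of 62% in both arms, the standard error of the difference is √(2 × 0.62 × 0.38 / 160) = 0.054, or 5.4 points.

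**The case against.** The best defence is that the any-duration wording only contrasts DCR with the clinical benefit rate defined just before it, which needs SD for at least 182 days. The second sentence of 8.4.4 also speaks of SD as the best response, and under Appendix 14.5 SD cannot be a best response before day 35. Taken together, the minimum would still apply.

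That works for the first sentence of 8.4.4 but not the second. Appendix 14.5 treats confirmed response and best response as the same thing. Extending DCR beyond patients whose confirmed best response is SD therefore has no effect unless it admits patients whose derived result is something else. Even if less was meant, two programmers could code the text differently.

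Several limits do stand:

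- Patients who stop early continue to be imaged. One later SD scan before new therapy removes the discrepancy.
- DCR is supportive and outside Type I error control (SAP 8.4), although it is tested at a nominal 0.05.
- The best-response table in 8.1.3 shows all categories by arm, so a reader could recover the stricter total for independent review in the Response Evaluable set.
- SAP section 12 lists changes from both the protocol and SAP version 1.4. It does not list this one, but version 1.4 is not available, so only the departure from the protocol can be checked.

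A reader might go further and infer that the rule favours the combination arm, because an added drug brings more early toxicity stops. The documents do not support that. Protocol 2.6 reports tolerability similar to either drug alone, and 6.1.2 calls discontinuation of balixafortide for toxicity rare. Severe infusion reactions leading to discontinuation of balixafortide (9.2.6.3) are a route open only in the combination arm, but no frequency is given. Unscheduled scans prompted by suspected progression could be more common in the control arm if the drug works, which would push the other way.

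**Conclusion.** The point holds. As written, SAP 8.4.4 conflicts with SAP 8.1.3, SAP 8.4 and Appendix 14.5, and with the minimum SD duration in the protocol. A patient whose only SD scan is before day 35, with no later SD scan before new therapy, counts as disease control while being NE or PD in best response.

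Each such patient adds about 0.63 points to that arm's DCR, assuming 160 per arm in ITT (3rd line+). The number of such patients and the balance between arms are unknown, so neither the size nor the direction of a between-arm bias can be stated. The 1-to-8 range is illustration only.

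It would be wrong to infer that every early toxicity stop with an EoT scan is miscounted, or that efficacy conclusions more widely are at risk. ORR counts only confirmed CR and PR, the clinical benefit rate has its own 182-day threshold, and PFS and OS do not use this rule.

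**What to change.** In SAP 8.4.4, define DCR as the proportion of patients whose derived best response is confirmed CR, confirmed PR or SD. Apply the SAP's minimum SD duration, under 8.1.3 for independent review and Appendix 14.5 for the investigator. State that NE and early PD count as no disease control. Remove the any-duration qualifier and the sentence that extends it.

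If the sponsor wants to keep the any-duration version, label it a sensitivity analysis and list it in SAP section 12.

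The cost is a short edit to one section and a slightly lower DCR. The separate difference between the protocol's day 42 and the SAP's day 35 is not resolved by this edit and is also absent from section 12.
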